**Outcomes:**

Primary outcome:

All-cause mortality at 28d

Secondary outcomes:

1. Time from intervention/control procedures starting to death (days & hrs)
2. Mean cardio-respiratory stability at 24h of intervention (aSCRIP score)
3. Prevalence of hypothermia ( $T < 36.5^{\circ}\text{C}$ ) at 24h of intervention
4. Mean daily weight gain (g/day) at 28d
5. Proportion of infants exclusively breastfeeding at discharge
6. Mean duration of hospital admission (days & hours)
7. Incidence of clinically suspected infection after 3 days and by 28 days or latest follow up
8. Prevalence of neonatal intestinal carriage of ESBL-Klebsiella pneumoniae at 28d

**Description of Study Design:**

This individually randomised, controlled, superiority trial will compare 2 parallel groups of hospitalised mild-moderately unstable preterm/LBW neonates receiving either early continuous skin-to-skin contact (<24h since admission) (intervention group) or standard care (control group) (ratio 1:1). Randomisation will be in random permuted blocks of varying sizes with allocation of twins to same arm. The intervention will be un-blinded to participants and researchers with blinding of outcomes where possible. Interventions will be maintained until hospital discharge and encouraged post-discharge with routine follow-up at 28 days. If participants become unwell whilst receiving the intervention and fulfil criteria for stopping, they will revert to standard care and re-commence skin-to-skin contact when stability criteria are met, in keeping with the control arm. Intention to treat analysis will be used.

Protocol #: 1

---

## 1 BACKGROUND INFORMATION AND RATIONALE

### 1.1 Background information

#### *Burden of neonatal & preterm/low-birth weight mortality*

Global neonatal mortality remains unacceptably high with the highest neonatal mortality rate (NMR) occurring in West and Central Africa region at 31/1000 live births and a large disparity in newborn survival between resource limited and resource rich regions. In contrast to impressive recent reductions in the global under-5 mortality rate, the NMR is declining at a much slower rate and neonatal deaths now account for 46% of all U5 deaths. The neonatal mortality rate (NMR) in The Gambia reduced from 50/1000 live births in 1990 to 28/1000 live births in 2016 but remains significantly higher than the Sustainable Development Goal (SDG) target of reducing NMR to <12/1000 live-births by 2030.

15 million babies are born preterm every year and complications of prematurity are the single largest direct cause of under-five mortality world-wide, causing 1.1 million deaths per year with a high burden of morbidity in survivors. In addition, low-birth weight (LBW) is an independent risk factor for neonatal mortality with the highest risk of death in those born preterm and small for gestational age (SGA). An estimated 14% of all Gambian babies are born preterm^9 and complications of preterm birth is the most common cause of death at the main neonatal referral centre in The Gambia. If SDG targets are to be met, a focus on feasible and effective hospital based management strategies for preterm babies in early neonatal period is critical to target the estimated 83% of prematurity related deaths occurring during this period.

#### *Kangaroo mother care is an evidence-based intervention for preterm/LBW hospitalised babies*

Kangaroo mother care (KMC) is recommended as standard care for all *stable*, hospitalised babies <2000g. It was developed in Colombia four decades ago and since adopted in both HIC and LMIC as an adjunct to incubator care. KMC is a complex intervention with the key component prolonged, continuous skin-to-skin contact between the nearly naked baby and mother's chest. The full definition, as described by Charpak et al, also includes promotion of early and exclusive breast-milk feeding, early discharge and close follow-up. Although other caregivers can provide skin-to-skin contact, a key aspect of KMC is the stimulation of maternal breast milk production and subsequent effects on feeding and growth.

Skin-to-skin contact and KMC are often used as synonyms in the literature, but for the purposes of this trial, early continuous skin-to-skin contact is considered the intervention under study.

Clinical benefits of KMC include reduced risk of: nosocomial infection; hypothermia, hypoglycaemia, severe infection and illness with moderate evidence of increased weight, length and head circumference gain and improved exclusive breast feeding at discharge, term and latest follow-up in *stable* neonates weighing less than 2000g. KMC also reduces duration of hospitalisation and hospital re-admission which benefits both neonate, mother and health care system. According to several systematic reviews, continuous KMC (>18h/day) reduces mortality by 36 - 51% compared to conventional incubator care. The most recent Cochrane review (2016) reported a 40% reduced risk of mortality at discharge or 40-41 weeks postmenstrual age (RR 0.60, CI 0.39-0.92; 8 trials, 1736 infants) and latest follow-up (RR 0.67, CI 0.48-0.85). However, this mortality effect is for "stable" neonates <2000g and there is an evidence gap for the mortality-effect of KMC in unstable babies within 24h after birth, when preterm/LBW babies undergo a physiological transition from in-utero to ex-utero life and are at greatest risk of mortality or near death events such as apnoea, hypoxia and bradycardia.

#### *Early, continuous skin-to-skin contact in unstable babies*

Early continuous skin-skin contact immediately after birth stabilises the newborn's cardio-respiratory system^17 but there is limited evidence for clinical and mortality effects in the unstable population. Clinical stability is variably defined in previous KMC studies with no standardised WHO definition or validated clinical model for resource limited settings. Of 20 RCTs

## Protocol #: 1

---

included in 3 systematic reviews, with mortality outcome at latest follow-up, KMC was initiated within mean or median 4 days of age in 7 studies and only 1 studied mortality effect as the primary outcome in unstable neonates (Table 1). Worku et al reported 40% reduction in mortality with early KMC in 123 neonates (22.5% vs 38%; p<0.05; RR0.59, 95% CI 0.34 – 1.03) but was underpowered with exclusion of >50% of eligible subjects, poorly defined case definitions and selective reporting of outcomes. There are no other published studies of early continuous skin-to-skin contact in unstable babies in resource limited settings with adequate power to examine mortality effect.

### *Understanding mechanistic pathways for benefit of early continuous skin-to-skin contact*

KMC works through multiple pathways, many of which are mediated by skin-to-skin contact triggering a primary neuro-endocrine mechanism involving oxytocin as a key mediator with systemic effects in both mother and neonate.

The key causal pathways underpinning the protective benefit of KMC are: thermal control; reduction in cortisol and stress response; cardio-respiratory stabilisation; enhanced breast milk supply and breast milk feeding and empowering the mother as key carer for her baby. Although previously extensively researched in stable babies receiving skin-to-skin contact, the validity and relative contribution of these pathways in early skin-to-skin contact is not fully known and this work would contribute towards understanding the physiological processes underpinning a potential benefit of early continuous skin-to-skin contact (early KMC).

Understanding how KMC reduces hospital acquired infections has not been widely researched, especially in resource limited settings where the bacterial burden and risk of nosocomial infections is high. Possibilities include: reduced exposure to environmental pathogens; protective effect of maternal microbiome and enhanced immunity through transfer of breast milk immune factors and/or microbiome. Late-onset infections in neonatal units of resource limited settings are predominantly due to gram-negative bacilli (GNB) and staphylococcus aureus, with GNB responsible for over 50% of all infections in hospital born neonates There is no data for the effect of KMC on GNB carriage and limited evidence that KMC alters the neonatal oral microbiome with decrease in Pseudomonas and increase in Streptococcus. This a unique and unexplored area of KMC research which may give insight into the reported 65% reduction in hospital acquired infection.

In summary, research into the clinical effects and safety of KMC, or continuous skin-to-skin contact in *unstable* babies has been highlighted as a research priority and warrants robust investigation to identify the mortality and clinical effects, safety and explore mechanisms underlying the potential protective effects of this feasible and life saving intervention.

### *Feasibility study to inform planning of eKMC*

From April to August 2017, a prospective observational feasibility study was conducted at the study site with the aims of understanding the target population and assessing the feasibility of conducting the clinical trial. From this data and previous published audit data from the study site, the clinical trial is considered feasible with an estimated 245 clinically eligible patients admitted per year. Barriers to recruitment are absence of caregiver within 24h of admission (21%), death or severe instability during screening period (23%) and consent refusal (14%). Mortality in eligible subjects at 28d is 56% (14/25) with median age at time of death 3d 2h and 71% (10/14) of all deaths occurred within the first week of admission. The feasibility study also identified key enablers and barriers to the provision of early KMC. These included maternal willingness to practice continuous KMC with good family support and the need for enhanced education of both health care workers and parents about providing early KMC alongside other medical interventions. These results will inform the sensitisation, planning and conduct of the clinical study.

References of literature and data are listed in Section 18.

Protocol #: 1

---

## 1.2 Rationale

Neonatal mortality remains unacceptably high and complications of prematurity are the most common, direct, cause of death in children aged under 5y. Feasible hospital based interventions to reduce mortality in resource limited settings are urgently needed.

The hospital management of preterm/LBW babies is challenging in resource limited settings, for multiple reasons, including: lack of essential newborn care and supportive management; high patient: health care worker ratios and increased risk of hospital acquired infections. Investigation and development of feasible, low cost strategies for the management of these babies within the critical early neonatal period is a global research and public health priority.

Kangaroo mother care is an evidence based and safe intervention currently used for stable newborns <2000g with significant mortality effect. Early, continuous skin-to-skin contact used in unstable newborns has the potential to improve survival through a combination of early and late mechanistic pathways, of which thermal control, cardio-respiratory stability and infection prevention control are the most important.

It is hypothesised that early continuous skin-to-skin contact in mild-moderately unstable neonates will improve survival by:

1. *Early onset, early* impact, stabilisation pathways which improve thermal control, promote cardio-respiratory stabilisation and modulate the natural history of preterm complications.
2. *Early onset, late* impact, pathways include prevention of late-onset infection, promotion of gastro-intestinal stability through improved breast milk feeding and improved recognition of apnoeic events needing resuscitation.

## 1.3 Potential risks and benefits

KMC is known to be a safe intervention for stable newborns and has multiple, evidenced based benefits including mortality and infection reduction (section 1.1.) Although the safety profile of early continuous skin-to-skin contact in resource limited settings with low level clinical monitoring is less well established, there is evidence from resource rich neonatal intensive care settings that using skin-to-skin care alongside other medical interventions is safe and well tolerated.

The potential risks to human subjects and known benefits are summarised in Section 14.3.

# 2 STUDY OBJECTIVES & OUTCOMES

## 2.1 Objectives

**Objective 1. To assess the effect of early continuous skin-to-skin contact on survival of hospitalised, mild-moderately unstable neonates weighing <2000g**

This will be achieved by measurement of the primary outcome of mortality at 28d and secondary outcomes of time to death..

**Objective 2. To assess the effect of early continuous skin-to-skin contact on other important clinical outcomes for hospitalised, mild-moderately unstable neonates weighing <2000g**

This will be achieved by measurement of the following secondary outcomes:

- Growth (weight)
- Duration of hospital admission

Protocol #: 1

---

- Suspected late onset infection

**Objective 3. To assess the safety of early continuous skin-to-skin contact in the hospital management of mild-moderately unstable neonates <2000g**

This will be achieved by measurement of the following secondary outcomes:

- Cardio-respiratory stability at 24h

**Objective 4. To explore causal pathways for the beneficial clinical effects of early continuous skin-to-skin contact compared to standard care in hospitalised, mild-moderately unstable neonates weighing <2000g**

This will be achieved by measurement of the following secondary process outcomes:

- Time to mortality
- Cardio-respiratory stability at 24h (early pathway)
- Hypothermia (early or late pathway)
- Exclusive breastmilk feeding at discharge (late pathway)
- Prevalence of intestinal ESBL-Klebsiella pneumoniae carriage (samples to be taken and stored, pending future funding)
- In addition and also as part of objective 4, carriage swab samples, environmental samples and blood/CSF culture isolates will be stored with the intention of undertaking the following work at a future stage, once additional funding is secured:
  1. Explore the effect of early skin-to-skin contact on neonatal intestinal/rectal microbiome, with comparison to maternal/caregiver microbiomes (16SrRNA)
  2. Describe the molecular epidemiology of ESBL-KP isolates, including clonal diversity and antibiotic resistance profile (whole genome sequencing)
  3. Compare neonatal carriage and invasive isolates with environmental isolates and maternal/caregiver carriage isolates to explore transmission of neonatal pathogens (whole genome sequencing)

## 2.2 Outcomes

Primary outcome:

All-cause mortality at 28d

Secondary outcomes:

1. Time from intervention/control procedures starting to death (days & hrs)
2. Mean cardio-respiratory stability at 24h of intervention (aSCRIP score)
3. Prevalence of hypothermia ( $T < 36.5^{\circ}\text{C}$ ) at 24h of intervention
4. Mean daily weight gain (g/day) at 28d
5. Proportion of infants exclusively breastfeeding at discharge
6. Mean duration of hospital admission (days & hours)
7. Incidence of clinically suspected infection after 3 days and by 28 days or latest follow up
8. Prevalence of neonatal intestinal carriage of ESBL-Klebsiella pneumoniae at 28d

Protocol #: 1

---

### **3. Study design**

#### **3.1 Type of study and design**

This individually randomised, controlled, superiority trial will compare 2 parallel groups of hospitalised preterm/LBW newborns receiving either early continuous skin-to-skin contact (started at 1 - 24h after birth)(intervention group) or standard care and late KMC (started at >24h) once clinically stable (control group) (ratio 1:1). The intervention will be un-blinded to participants and researchers with blinding to outcomes, where possible. Interventions will be maintained until hospital discharge and encouraged post-discharge with daily in-patient review and follow up at 28 days. If participants meet criteria of being severely unstable (definitions, page 10) whilst receiving the intervention they will revert to standard care and re-commence KMC when stability criteria are met, in accordance with current standard care (section 7). Primary analysis of primary and secondary outcomes will be on an intention to treat basis. A pragmatic study design will be used with a standardised preterm/LBW clinical management protocol based on current standard care and provided by study site staff. In-order to explore the infection prevention control mechanisms underpinning this intervention, paired maternal /caregiver swab samples will be taken at time of admission in addition to environmental swab samples.

#### **3.2 Setting**

The study will be conducted at the neonatal unit of Edward Francis Small Teaching Hospital (EFSTH), with technical and laboratory support from MRC Unit, The Gambia (MRCG).

The neonatal unit is the major referral unit in The Gambia, accepting in-born and out-born admissions. Approximately 1400 neonates are admitted annually, of which 25% weigh <2000g and are aged <24h.(unpublished) The overall case fatality rate is 38% with very low birth weight (VLBW) a risk factor for mortality and 58% case fatality rate in neonates weighing <1500g. This is consistent with feasibility study data reporting a 28d mortality rate of 56% in neonates who would be eligible for the clinical trial. (unpublished)

Current standard care for preterm/LBW neonates includes care under incubator or radiant heaters; oxygen via concentrators; nasal CPAP; IV fluids given by burette if available; IV caffeine; IV ampicillin, gentamicin, cloxacillin, metronidazole and ceftriaxone. Continuous monitoring is not available but twice daily temperature and once daily vital signs, including oxygen saturation and blood glucose, are done routinely on critical patients. Neonates <2000g currently receive intermittent KMC for minimum 60 minutes, 4 – 5 times a day once they are stable and off oxygen. They are admitted to the KMC unit for continuous KMC when not receiving IV medications or fluids. There are unit guidelines and monitoring documents available and the study site staff have been trained in KMC theory and practices.

#### **3.3 Randomisation and blinding procedures**

##### **3.3.1. Randomisation**

Randomisation will be performed by an independent statistician with computer generated random number tables to give a random allocation of numbers in permuted blocks of varying block sizes. Stratification by admission weight categories will be used with separate random number tables if <1200g or ≥1200g. Allocation concealment will be performed with opaque, sealed envelopes labelled consecutively with the randomisation number (RN00X) and containing a piece of paper stating the randomisation number and the treatment allocation. A research clinician or nurse not connected to the study will prepare the envelopes. The envelopes will be securely kept in a cabinet at the study site office. Following the screening process and collection of baseline data, treatment allocation will take place according to the content of the sealed envelope, in consecutive order of randomisation number. Prior to opening the envelope, the date, time and unique study ID of the baby

Protocol #: 1

---

will be written on the outside of the envelope and the envelope will be stored for later auditing. Subjects who are of twin birth and completed twin admissions will be allocated to the same arm, according to the twin that was declared eligible first. A randomisation log will be kept to ensure that the randomisation procedure is correctly followed.

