#### 4.2.1. Inclusion criteria

Neonates:

- New admission to the neonatal unit at EFSTH during the study period
- Admission weight less than 2000g
- Age 1 – 24h at time screening begins
- Alive at time of enrolment
- Singleton or completed twin birth admission
- Written informed consent provided by a parent/caregiver

Mother/caregiver:

- Paired neonate is enrolled in the study
- Is available and willing to provide continuous skin-to-skin contact
- Provides written informed consent

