At the end of the 10 minute period, if the baby meets all of the stable criteria they will be excluded and receive standard care. If criteria for mild instability are present, the subject will be recruited. If moderate or severe instability is present (definitions, page 10), continuous pulse oximetry will continue for further 2h 50 minutes (3 hours total) with a manual assessment of respiratory rate and breathing pattern at 3 hours. If the neonate meets any criteria of severe instability at any stage of the screening process, they will receive immediate medical management but will be excluded from the study only

Protocol #: 1

---

if they continue to meet severe criteria at the 3h assessment. All babies will receive standard medical management (E.g. oxygen, IV fluids, IV antibiotics) as indicated by the study site staff and standardised management protocol. All screening procedures will be documented on the screening log, which will record all new admissions weighing <2000g who undergo screening procedures and the outcome of the assessment. An eligibility checklist and flow chart will be used to assist the screening process. A screening number will be allocated.

It is estimated to take between 30 minutes and 3h 20 minutes to complete the screening process (Appendix 1. Overview of screening and enrolment procedures).

If the baby meets eligibility criteria but the caregiver is not present within 3h of the screening procedures, the 10 minute observation of cardio-respiratory stability will be repeated and documented once the caregiver is available and prior to informed consent. This is to ensure that the baby has not deteriorated in the intervening period.

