**14.5.2 Informed consent for neonatal participation**

*Timing of consent*

Written, informed consent will take place as soon as possible following screening procedures and prior to randomisation.

*Content of informed consent*

Informed consent will be taken for the following: neonatal inclusion in the study; randomisation and receipt of the intervention; provision of continuous skin-to-skin contact if allocated to the intervention arm; collection of socio-demographic data; collection of clinical data; collection of biological samples and follow-up.

Protocol #: 1

*Person providing informed consent on behalf of the subject*

[figure not shown]
The preferred person to provide informed consent is the parent, but it is recognised that this may not be possible within the time-frame, as outlined in section 14.5.1. If the parent is not available within defined time points (figure 3), it will be explored if there is any relative available. The relative, or caregiver, will then consent on the parents behalf, obtaining verbal permission from the parents via telephone contact if the caregiver wishes. A Statement of Guardianship form will be completed to document the details and relationship of the guardian to the baby. Once the parent is available at the study site, parental informed consent will be obtained to ensure that they agree for the baby to continue in the study.

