## **3.2 Randomisation & allocation**

An independent statistician generated a randomisation sequence using VBA (Visual Basic Application) within an Access database to produce two random number tables with stratification by admission weight categories (<1200g; ≥1200g). Random permuted blocks of varying sizes were used with 1:1 allocation. Allocation concealment was performed with sequentially numbered, opaque, sealed envelopes prepared by an independent researcher and accessible to study team only. Following collection of baseline data, the study nurse opened the next numbered envelope for the correct weight category. The participant identifier, date and time were recorded on the outside of the envelope prior to opening, to identify any subversion of allocation sequence. Twins were allocated to the same arm, according to the first eligible twin's weight.

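### A co-twin whose eligibility or consent is settled after the pair's envelope is opened can be enrolled with the arm known, and the SAP has no sensitivity analysis for this

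*Protocol*

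**What the plan says.** - **Allocation of twins.** Protocol 3.3.1 gives both twins a single arm, "according to the twin that was declared eligible first". SAP 3.2 agrees ("Twins were allocated to the same arm") and takes the weight stratum from the first eligible twin. Protocol 4.2.1 admits "Singleton or completed twin birth admission", so both babies of a pair can be enrolled.
- **Order of steps.** Protocol 3.3.1: "Following the screening process and collection of baseline data, treatment allocation will take place according to the content of the sealed envelope". Protocol 14.5.2 places consent "as soon as possible following screening procedures and prior to randomisation". Both rules are worded for a single baby.
- **Length of screening.** Protocol 5.3.2 decides on a mildly unstable baby at 10 minutes: "If criteria for mild instability are present, the subject will be recruited". A moderately or severely unstable baby stays on oximetry for 3 hours in total before the decision.
- **Blinding.** Protocol 3.3.2 accepts that families and staff will know the arm.
- **Analysis.** SAP 6.2 handles twins through generalised estimating equations, a frailty term, covariate adjustment and a singleton/twin subgroup. Its only sensitivity analysis removes babies recruited in error.

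**The concern.** A sealed envelope protects a baby only if the decision to enrol that baby is made before the envelope is opened. For a pair, one envelope fixes two allocations. If the second baby's eligibility or consent is still open at that point, the people deciding already know which arm the baby will enter.

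The documents suggest why the arm could matter to that decision. Protocol 4.2 excludes severely unstable babies partly because continuous skin-to-skin contact is hard to deliver to them. That consideration bears on a borderline co-twin headed for the intervention arm but not on one headed for control. A caregiver asked to give at least 18 hours of contact a day to a second baby also faces a different choice from a caregiver in the control arm.

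If co-twins entering the two arms differed in prognosis, the 28-day mortality comparison would be biased. Analysis by intention to treat would not correct this, because it starts from the babies enrolled. Methods for within-pair correlation do not correct it either.

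**Working it through.** **1. Does any rule close the gap?** Set side by side, Protocol 3.3.1, 5.5, 5.6 and 14.5.2 and SAP 3.2 all place the envelope after screening, consent and baseline data, but for one baby at a time. The twin rule speaks of a twin declared eligible first, which implies a sequence. The requirement about twin admissions concerns admission, not screening. No section makes the envelope wait for the second baby, and none says whether one consent covers both.

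**2. How long is the gap?** Times are from Protocol 5.3.2 and Appendix I, with both twins starting screening together.
- Mildly unstable first twin, fastest path to the end of randomisation: checks 20 + observation 10 + consent 40 + enrolment 5 + baseline 30 + swabs 10 + randomisation 10 = 125 min = 2 h 05 min. Adding 5 min for identification and 10 min for sensitisation gives 2 h 20 min, the minimum stated in Appendix I.
- Observed co-twin, end of screening: 20 min + 3 h = 3 h 20 min, the maximum stated in 5.3.2.
- Gap in the eligibility decision: 3 h 20 min − 2 h 05 min = 1 h 15 min.
- The gap closes if the first twin's consent takes 40 + 75 = 115 min = 1 h 55 min, which is inside the stated range of 40 min to 3 h.

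A co-twin whose screening starts later, or whose consent is taken separately and later, can still be exposed.

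**3. What could be influenced?** Respiratory rate and breathing pattern are assessed by hand (5.3.2). Chest in-drawing and a clinical decision that CPAP is needed both enter the stability classes (Definitions). Caregiver willingness and written consent are required (4.2.1).

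**4. How many babies?** The denominator is the plan's 392, which reproduces. With 48% against 0.70 × 48% = 33.6% (mean 40.8%), 80% power and alpha 0.05 (two-sided assumed):
- n = [1.96√(2 × 0.408 × 0.592) + 0.842√(0.48 × 0.52 + 0.336 × 0.664)]² / 0.144² = 181.7 per arm
- with continuity correction, (n/4)[1 + √(1 + 4/(0.144n))]² = 195.3, so 196 per arm and 392 in total.

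The documents give no twin share. Assuming 20% to 40% of babies are in enrolled pairs, second twins number 392 × 0.20/2 = 39 to 392 × 0.40/2 = 78, or 10% to 20% of the total. This counts every second twin as exposed, so it is a ceiling.

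**5. How much bias?** This is an illustration only. Let a share t of each arm be exposed co-twins, and let selection shift their mortality by s between arms. Bias in the risk difference is b = t × s. With 48% mortality and 196 per arm, SE = √(2 × 0.48 × 0.52/196) = 0.0505. The two-sided type I error is Φ(−1.96 + b/SE) + Φ(−1.96 − b/SE), ignoring clustering.

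| t | s (points) | b (points) | b as % of planned 14.4 | Type I error |
|---|---|---|---|---|
| 5% | 5 | 0.25 | 1.7 | 0.0503 |
| 10% | 10 | 1.0 | 6.9 | 0.0545 |
| 20% | 20 | 4.0 | 27.8 | 0.1245 |

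**The case against.** The strongest reply has four parts.

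- **The window is narrow.** A reader might infer from the 10-minute and 3-hour figures that the envelope opens after 10 minutes and leaves a gap of almost 3 hours. Appendix I does not support that: consent, baseline data and swabs come first, and the gap can close. This stands, but it narrows the exposure without removing it.
- **Many pairs are not exposed by the observation rule.** Two mildly unstable twins are both decided at 10 minutes, and two moderately unstable twins both wait 3 hours. Co-twins who are stable, or still severe at 3 hours, are excluded. Exposure by this route needs a discordant pair with the faster twin first. This also stands, and it is why 39 to 78 cannot be read as an estimate.
- **Discretion is limited.** Oximetry is recorded, the cut-offs are numeric, ties have a rule, and caregiver willingness is required before the first twin enters. This reduces the room for selection. The clinical judgements and the second consent remain.
- **The SAP already has a clean estimate.** The singleton subgroup in 6.2 covers all outcomes, with confidence intervals and an interaction test, and this route cannot affect it. That is a real safeguard. It also discards first twins and concealed co-twins, so it is a smaller and different population from all babies enrolled under concealment. SAP 5.1 compares recruited with eligible unrecruited babies, but not by arm.

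**Conclusion.** The point holds in a limited form. The plan as written lets some second twins enter with the arm known, and no planned analysis isolates them. A reader might go further and infer that concealment failed for the trial, or that the mortality result is biased. The documents support neither: singletons, first twins and co-twins settled before the envelope are protected by sequentially numbered, opaque, sealed envelopes marked with date and time, and nothing shows that selection took place.

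The size is unknown. The 39 to 78 rests on an assumed twin share and on every second twin being exposed. Under the illustrative assumptions the middle case is small (1.0 point, type I error 0.0545). Only the extreme case, with 20% exposed and a 20-point shift, gives 4.0 points and 0.1245. The point warrants one added sensitivity analysis, not a change to the primary analysis.

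**What to change.** **SAP 6.2, sensitivity analysis.** Repeat the primary outcome analysis excluding co-twins whose eligibility or consent was settled after the date and time on the pair's envelope. Whether a co-twin was still unsettled when the envelope opened is fixed before the arm is revealed, so this exclusion does not itself depend on the arm.

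The documents promise a date and time only for the envelope (Protocol 3.3.1, SAP 3.2). They promise a screening log and a record of consent, but no clock time for each eligibility or consent decision. If those times were not captured, exclude all second-eligible twins.

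**Reporting.** Give, by arm, the number of co-twins screened, excluded, refused and enrolled after the first twin's allocation.

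**Cost.** A small loss of precision in the sensitivity analysis and a little extra analysis work. SAP 3.5 says the plan is to be posted before the database closes and before any analyses, so the addition can still be pre-specified.

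**Future trials.** SAP 3.1 dates the trial May 2018 to April 2020, so a procedural change comes too late here. A later trial with this design could record both admitted twins' eligibility and consent decisions before opening the pair's envelope, at the cost of some delay in randomising the first twin.
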